9.3.3 Analysis of Other Secondary Variables

9.3.3.1 Definition of Variables

Time-to-first PEx through Week 24: the number of days from the first dose date of study drug to the date of the first pulmonary exacerbation during the PEx analysis period. A subject who does not experience a PEx during the PEx analysis period will be censored at the PEx analysis period end date.

BMI z-score: the BMI score, adjusted for age and sex, will be referred to as BMI-for-age z-score (BMI z-score). The BMI z-score will be calculated by using Centers for Disease Control and Prevention (CDC) growth charts⁸, with the age (in months) used for the calculation defined in [Appendix A](#).

9.3.3.2 Analysis Method

Time-to-first PEx through Week 24: Time-to-first PEx will be analyzed using the Cox regression model. The model will include a fixed effect for treatment, as well as continuous baseline ppFEV₁, age at screening (<18 versus \geq 18 years of age), and sex (male versus female) as

[figure not shown]
covariates. Additionally, the Kaplan-Meier method will be used to estimate the cumulative exacerbation-free rate by treatment group; the associated plot will be provided.

Note: If the number of events is <5 in either treatment group, Cox regression will not be performed and the analysis of the time-to-first PEx will be restricted to the Kaplan-Meier method.

Absolute change in BMI z-score from baseline at Week 24 (for subjects ≤ 20 years of age at Baseline): Analysis of this variable will be based on an MMRM similar to the analysis of the primary efficacy variable, excluding the covariate of age at screening (<18 versus ≥ 18 years of age), for subjects ≤ 20 years of age at Baseline. Data obtained from Day 15, Week 4, Week 8, Week 12, Week 16, and Week 24 Visits will be included in the model.

Absolute change in body weight from baseline at Week 24: Analysis of this variable will be based on an MMRM similar to the analysis of the primary efficacy variable. Data obtained from Day 15, Week 4, Week 8, Week 12, Week 16, and Week 24 Visits will be included in the model.

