9.2 Method of Assigning Subjects to Treatment Groups

Subjects will be randomized (1:1) to the TC VX-445/TEZ/IVA arm or to the triple placebo arm. Randomization will be stratified by ppFEV₁ determined during the Screening Period (<70 versus ≥70), age at the Screening Visit (<18 versus ≥18 years of age), and sex (male versus female).

An interactive web response system (IWRS) will be used to assign subjects to treatment. The randomization code list will be produced by Vertex Biometrics or a qualified randomization vendor.

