12.3.3.1 Final Analysis

12.3.3.1.1 Analysis of Primary Variables

The primary efficacy variable is the absolute change in ppFEV₁ from baseline at Week 4. The analysis of this variable will be performed using a mixed-effects model for repeated measures (MMRM) with change from baseline at Day 15, Week 4, Week 8, Week 12, Week 16, and Week 24 as the dependent variable. The model will include treatment group, visit, and treatment-by-visit interaction as fixed effects, with continuous baseline ppFEV₁, age at screening (<18 versus ≥18 years of age) and sex (male versus female) as covariates. The model will be estimated using restricted maximum likelihood. Denominator degrees of freedom for the *F* test for fixed effects will be estimated using the Kenward-Roger approximation. An unstructured covariance structure will be used to model the within-subject errors. If the model estimation does

not converge, a compound symmetry covariance structure will be used instead. Conditional on the observed data and covariates, missing data will be assumed to be missing at random; consequently, no imputation of missing data will be performed.

The primary result obtained from the model will be the estimated treatment difference at Week 4. The adjusted mean difference at Week 4 with 2-sided 95% confidence intervals and 2-sided *P* values will be provided. Furthermore, the adjusted mean and treatment difference at each post-baseline visit will also be provided, obtained from the model.

Sensitivity analyses for handling missing data will be described in the SAP.

Supportive analyses and subgroup analyses of the primary efficacy variable will also be described in the SAP.

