- **Absolute change in CFQ-R respiratory domain score from baseline at Week 4:** Analysis of this variable will be based on an MMRM model similar to the analysis of the primary efficacy variable. Data obtained from the Week 4, Week 8, Week 12, and Week 24 Visits will be included in the model to estimate the treatment effect at Week 4.

The key secondary endpoints will be formally tested only during the final analysis when all subjects have completed study participation and the primary endpoint is statistically significant either at the IA or at the final analysis. Additional details will be provided in the SAP.

Analysis of Other Secondary Variables

Other secondary efficacy variables include:

- **Time-to-first PEx through Week 24:** Time-to-first PEx will be analyzed using the Cox regression model. The model will include a fixed effect for treatment, as well as continuous baseline ppFEV₁, age at screening (<18 versus ≥18 years of age), and sex (male versus female) as covariates. A subject who does not experience a PEx during the PEx analysis period will be censored at the PEx analysis period end date. If the proportional hazards assumption is violated for any of the categorical covariates, a stratified Cox regression will be conducted. Additionally, the Kaplan-Meier method will be used to produce a graphical presentation of the cumulative exacerbation-free survival rate for each treatment group and to estimate the cumulative exacerbation-free survival rate by treatment group. Note: If the number of events is <5 in either treatment group, Cox regression will not be performed and the analysis of the time-to-first event will be restricted to the Kaplan-Meier method.
- **Absolute change in BMI z-score from baseline at Week 24 (for subjects ≤20 years of age at Baseline):** Analysis of this variable will be based on an MMRM model similar to the analysis of the primary efficacy variable, for subjects ≤20 years of age at Baseline. Data obtained from Day 15, Week 4, Week 8, Week 12, Week 16, and Week 24 Visits will be included in the model.
- **Absolute change in body weight from baseline at Week 24:** Analysis of this variable will be based on an MMRM model similar to the analysis of the primary efficacy variable. Data obtained from Day 15, Week 4, Week 8, Week 12, Week 16, and Week 24 Visits will be included in the model.

Additional details will be provided in the SAP.

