3 MODIFICATIONS

3.1 Modifications to the Approved Clinical Study Protocol

Not Applicable.

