9.3.2.2 Analysis Method

Absolute change in ppFEV₁ through Week 24: Analysis of this variable will be based on an MMRM that is exactly the same as the primary efficacy variable. However, the Day 15 Visit will not be included in the estimation of the average treatment effect through Week 24 as the treatment effect is not expected to reach the steady state at Day 15.

Number of PEx through Week 24: Analysis of this variable will be performed using a negative binomial regression model with a fixed effect for treatment, as well as continuous baseline ppFEV₁, age at screening (<18 versus ≥18 years of age), and sex (male versus female) as covariates. The logarithm of the subject-specific PEx analysis period duration (in years) will be treated as the offset in the model.

Absolute change in SwCl from baseline through Week 24: Analysis of this PD variable will be based on an MMRM similar to the analysis of the primary efficacy variable. Data obtained from Week 4, Week 8, Week 12, and Week 24 Visits will be included in the model and all of these visits will be included in the estimation of the average treatment effect through Week 24.

Absolute change in the CFQ-R respiratory domain score from baseline through Week 24: Analysis of this domain will be based on an MMRM similar to the analysis of the primary efficacy variable. Data obtained from Week 4, Week 8, Week 12, Week 16, and Week 24 Visits will be included in the model and all of these visits will be included in the estimation of the average treatment effect through Week 24.

Absolute change in BMI from baseline at Week 24: Analysis of this variable will be based on an MMRM similar to the analysis of the primary efficacy variable. Data obtained from Day 15, Week 4, Week 8, Week 12, Week 16, and Week 24 Visits will be included in the model.

Absolute change in SwCl from baseline at Week 4: Analysis of this PD variable will be based on an MMRM similar to the analysis of the primary efficacy variable. Data obtained from Week 4, Week 8, Week 12, and Week 24 Visits will be included in the model to estimate the treatment effect at Week 4.

Absolute change in CFQ-R respiratory domain score from baseline at Week 4: Analysis of this domain will be based on an MMRM similar to the analysis of the primary efficacy variable. Data obtained from Week 4, Week 8, Week 12, Week 16 and Week 24 Visits will be included in the model to estimate the treatment effect at Week 4.

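### The SAP drops the age stratification factor from the BMI z-score model without giving a reason; this costs a little precision on an endpoint that carries no alpha

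*SAP*

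**What the plan says.** **BMI z-score.** Protocol 12.3.3.1.2 specifies an MMRM "similar to the analysis of the primary efficacy variable, for subjects ≤20 years of age at Baseline". The primary model it points to (Protocol 12.3.3.1.1) is fitted "with continuous baseline ppFEV₁, age at screening (<18 versus ≥18 years of age) and sex (male versus female) as covariates". SAP 9.3.3.2 takes the same model for the same subjects, "excluding the covariate of age at screening", and gives no reason. Protocol 9.2 stratifies randomization by screening ppFEV₁, "age at the Screening Visit (<18 versus ≥18 years of age), and sex (male versus female"; SAP 7.3 repeats this.

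**CFQ-R at Week 4.** For this endpoint Protocol 12.3.3.1.2 states: "Data obtained from the Week 4, Week 8, Week 12, and Week 24 Visits will be included in the model". The corresponding line in SAP 9.3.2.2 lists five visits, adding Week 16. These are the same five visits that the SAP uses for CFQ-R through Week 24: "Data obtained from Week 4, Week 8, Week 12, Week 16, and Week 24 Visits will be included in the model".

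**Time-to-first PEx.** The protocol says that if proportional hazards fails for a categorical covariate, "a stratified Cox regression will be conducted". SAP 9.3.3.2 repeats the Cox model, the Kaplan-Meier estimate and the rule for fewer than five events, but not this sentence.

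**Declared changes.** SAP 3.1, on modifications to the protocol, reads "Not Applicable". Section 3.1 of Addendum 2 says the same.

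**The concern.** A factor used to stratify randomization normally stays in the analysis model. If it is prognostic and is left out, variation between strata moves into the residual and the standard error is larger than the design requires. Here the term is not redundant. The trial enrols from age 12, so subjects aged 20 or less at baseline include both 12-to-17-year-olds and 18-to-20-year-olds. Standardizing the level of BMI for age does not make its 24-week change the same in adolescents and young adults.

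At stake is some precision for BMI z-score. There is also a question of record: a reader who relies on SAP 3.1 would not learn that this model, the CFQ-R Week 4 visit list and the Cox fallback differ between the two documents.

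**Working it through.** The documents give no SD, power or expected number of subjects for BMI z-score, and no power or SD for CFQ-R at Week 4. There is therefore no planned figure to reproduce. The check is a comparison of texts plus an estimate of size.

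**1. Is the age term constant in the analysed subset?** No. The subset is defined by age ≤20 at baseline and the term splits at 18. SAP 9.3.1.5 drops age from the age-subgroup models and sex from the sex-subgroup models, where each is constant within a category. That reason does not carry over.

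**2. Does the age adjustment of the z-score explain the omission?** SAP 9.3.3.1 defines the z-score as adjusted for both age and sex. By that logic sex would go too, but only age is removed.

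**3. Size for BMI z-score.** Let R² be the share of the variance of change explained by age stratum beyond the other covariates (assumed). Omitting the term multiplies the standard error by 1/√(1 − R²), and the equivalent share of the subset's sample lost is R².

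- R² = 0.01: 1/√0.99 = 1.005, so 0.5% larger; 1% of the sample
- R² = 0.03: 1/√0.97 = 1.015, so 1.5% larger; 3% of the sample
- R² = 0.05: 1/√0.95 = 1.026, so 2.6% larger; 5% of the sample
- R² = 0.10, as an outer value: 1/√0.90 = 1.054, so 5.4% larger; 10% of the sample

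**4. Direction.** The subset is defined by a baseline characteristic, so the randomized comparison stays valid without the term. The loss is one of precision.

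**5. CFQ-R at Week 4: does the visit list matter numerically?** Trials were simulated with 180 per arm and dropout of 5% at Week 4 rising to 10% at Week 24 (the planning figures). Each was fitted with an unstructured-covariance model by maximum likelihood with a Wald test, once with four visits and once with five. The following were assumed and are not in the documents: SD 16, within-subject correlation 0.4 or 0.7, intermittent missingness 0 or 5%, true difference 0 or 3.5 points. That makes eight settings of 60 replicates each.

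- Mean ratio of standard errors, five visits to four: 0.999 to 1.000
- SD of the shift in the Week 4 estimate: 0.02 to 0.08 points; largest single shift 0.28
- Decision at 0.05 changed: 0 of 60 in six settings and 1 of 60 in two, so 2 of 480 overall

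Sixty replicates per setting give only a rough rate of changed decisions, but the estimates and standard errors barely move.

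**The case against.** The protocol leaves room for the SAP. Section 12 calls itself a summary, and the passage on other secondary endpoints defers further detail to the SAP. For BMI z-score the protocol asks only for a model similar to the primary one, whereas for ppFEV₁ through Week 24 it requires an identical model. Dropping age could therefore be read as elaboration, and on the argument above the omission is conservative. All of this stands, and it is why the point is small. It does not supply a reason for removing age while keeping sex.

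A reader might infer something stronger: that a formally tested endpoint has two competing models and two P values to choose from. The documents do not support that. BMI z-score is not in the hierarchy of SAP 9.3.2.3. CFQ-R at Week 4 is in it, but the protocol's missing Week 16 looks like a drafting slip: Table 3-2 schedules CFQ-R at Week 16, and the protocol's own through-Week-24 CFQ-R model includes it. The SAP gives one complete model and was to be final before the interim data lock. The endpoint is seventh and last, so no later test depends on it.

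Nor does the Cox omission create a rival analysis. The main Cox model is the same in both documents; only a conditional fallback is missing.

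Finally, Addendum 2 cites a SAP Version 1.1 EUR and an Addendum 1. The SAP supplied describes itself as the first version, and Addendum 1 is not supplied, so whether either deals with these items cannot be checked.

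**Conclusion.** The point holds as a minor one. SAP 9.3.3.2 removes a randomization stratum from the BMI z-score model although the analysed subjects span it, and no reason in the documents fits. The cost is a standard error 0.5 to 2.6% larger than necessary if age stratum explains 1 to 5% of the variance of change. That range is an assumption. The endpoint carries no alpha, type I error is not inflated, and no formal conclusion of the trial depends on it.

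The CFQ-R visit list and the Cox fallback are separate documentation points. The first touches a formally tested endpoint, but with almost no numerical effect under the simulated conditions. The second omits a safeguard for an endpoint outside the hierarchy; it extends to the other time-to-first-event analyses in SAP 9.3.4.3, which refer back to the same section.

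**What to change.** - In SAP 9.3.3.2, delete the clause that excludes age at screening, so that the BMI z-score model keeps the age stratum as the protocol's model does. This costs one degree of freedom and needs no new data.
- In SAP 3.1, state that the SAP's five-visit model governs CFQ-R at Week 4. This settles the mismatch without a protocol modification, which under Protocol 13.2.3 the sponsor would have to submit to the regulatory authorities.
- Restore the stratified Cox sentence in SAP 9.3.3.2, or record its omission in SAP 3.1.

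The cost is a few lines of SAP wording. Sample size, alpha and the testing order are unaffected.

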9.3.4 Analysis of Additional Efficacy Variables

9.3.4.3 Analysis of Additional Variables for Pulmonary Exacerbations and Hospitalization

The analysis period for all variables in this section will be the same as the PEx analysis period.

Pulmonary Exacerbations

In addition to the key secondary endpoints, PEx will be further analyzed as described below:

- Time-to-first event (time in days):
 - Time-to-first PEx requiring hospitalization
 - Time-to-first PEx requiring IV antibiotic therapy
 - Time-to-first PEx requiring hospitalization or IV antibiotic therapy
- Number of events
 - Number of PEx requiring hospitalizations
 - Number of PEx requiring IV antibiotic therapy
 - Number of PEx requiring hospitalization or IV antibiotic therapy
- Duration of events:
 - Number of days with PEx
 - Number of days with PEx requiring hospitalization
 - Number of days with PEx requiring IV antibiotic therapy
 - Number of days with PEx requiring hospitalization or IV antibiotic therapy.

Hospitalization

- Number of events:
 - Number of planned hospitalizations for CF (i.e., antibiotic therapy)
 - Number of all unplanned hospitalizations for reasons other than antibiotic therapy for sinopulmonary signs/symptoms
- Duration of events
 - Number of days of all unplanned hospitalizations for reasons other than antibiotic therapy for sinopulmonary signs/symptoms

For the time to event variables, the analysis time will be the number of days from the first dose date of study drug to the date of the first defined event during the PEx analysis period. A subject who does not experience the event during the PEx analysis period will be censored at the PEx analysis period end date for that event.

For the number of events variables, subjects with multiple defined events during the PEx analysis period will be counted multiple times. The annualized duration of events for each subject will be the total number of days with the defined events times 48 weeks divided by the total number of weeks on study up to the end of the PEx analysis period.

Analysis of Pulmonary/Hospitalization Variables

Time-to-first event: the time-to-first event endpoints will be analyzed similarly to the analysis of time-to-first PEx described in Section 9.3.3.2.

Note: If the number of subjects with events is <5 in either treatment group, Cox regression will not be performed and analysis of time-to-first event will be restricted to Kaplan-Meier methods.

Number of events: the number of events will be analyzed using negative binomial regression similar to the analysis of number of PEx described in Section 9.3.2.2.

Note: If the number of events is <5 in either treatment group, negative binomial regression will not be performed and analysis of event counts will be based on a Fisher's Exact test.

Duration (number of days): the annualized duration of events will be analyzed using a stratified (by ppFEV₁ at screening (<70 versus ≥70), age at screening (<18 versus ≥18 years of age), and sex (male versus female)) Wilcoxon rank-sum test to assess the difference between treatment groups.

9.4 Safety Analysis

All safety analyses will be based on data from the TE period for all subjects in the Safety Set. Subjects will be analyzed according to the treatment they actually received in the Treatment Period. For subjects receiving study drug from more than one treatment group, the treatment group allocation will be the higher treatment group (VX-445/TEZ/IVA > TC Placebo).

The overall safety profile of the study drug will be assessed in terms of the following safety and tolerability endpoints:

- Treatment-emergent adverse events (TEAEs)
- Clinical laboratory values
- ECGs
- Vital signs
- Pulse oximetry

Only descriptive analysis of safety will be performed and no statistical testing will be performed.

9.4.1 Adverse Events

For analysis purposes, AEs will be classified as pretreatment AEs, TEAEs, or post-treatment AEs, defined as follows:

Pretreatment AE: any AE that occurred before the first dose date of study drug

TEAE: any AE that worsened (either in severity or seriousness) or that was newly developed at or after the first dose date of study drug through the end of the TE period

Post-treatment AE: any AE that worsened (either in severity or seriousness) or that was newly developed after the TE period

For AEs with completely missing or partially missing start dates, if there is no clear evidence that the AEs are pre-treatment or post-treatment, the AEs will be classified as TEAEs.

Details for imputing missing or partial start dates of adverse events are described in [Appendix E](#).

An overview of all TEAEs by treatment group and overall will be summarized in the following categories:

- Number of TEAEs (total number of TEAEs only)
- Subjects with any TEAEs
- Subjects with TEAEs by strongest relationship
- Subjects with TEAEs by maximum severity
- Subjects with TEAEs leading to study drug discontinuation (discontinuation of any study drug)
- Subjects with TEAEs leading to study drug interruption (interruption of any study drug)
- Subjects with Grade 3/4 TEAEs
- Subjects with related TEAEs
- Subjects with serious TEAEs
- Subjects with related serious TEAEs
- Subjects with TEAE leading to death

The following summary tables of TEAEs will be presented by treatment group:

- All TEAEs
- Grade 3/4 TEAEs
- TEAEs by strongest relationship
- TEAEs by maximum severity
- TEAEs leading to treatment discontinuation
- TEAEs leading to treatment interruption
- Related TEAEs
- Serious TEAEs
- Related serious TEAEs
- TEAEs leading to death

Summaries will be presented by MedDRA SOC and PT using frequency counts and percentages (i.e., number and percentage of subjects with an event). When summarizing the number and percentages of subjects, subjects with multiple occurrences of the same adverse event or a continuing adverse event will be counted once, and only the maximum severity level will be presented in the severity summaries, and the strongest relationship level in the relationship summaries.

Additional summary tables will be presented by treatment for TEAEs showing number and percentage of subjects

- All TEAEs by PT

All AEs, including pretreatment AEs, TEAEs, and post-treatment AEs, will be presented in an individual subject data listing based on the All Subjects Set. In addition, a listing containing individual subject adverse event data for TEAEs leading to treatment discontinuation, TEAEs leading to treatment interruption, Grade 3/4 TEAEs, SAEs and all deaths will be provided separately, with a flag indicating the TEAE status for SAEs and deaths.

For all AEs, the eCRF captures the action taken for VX-445/TEZ/IVA pills separately from the action taken for IVA monotherapy pills. As a result, it is possible that, in the final database (after database lock), the AE actions taken for the two agents (fixed dose VX-445/TEZ/IVA and ivacaftor monotherapy) are different. The summaries and listings of “AE Leading to Treatment Discontinuation” and “AE Leading to Treatment Interruption” account for discontinuation and interruptions for either agent.

